### **Part 2: Chronic Hepatitis B Patients**

Approximately 20-30 virologically suppressed CHB patients may be randomized into at least two cohorts in Part 2 of the study (Cohort 3 will be optional) and up to 15 treatment-naïve CHB patients may be randomized into the optional Cohort 4. Within each dose level, up to 15 patients (8-12 active and 2-3 placebo) will be randomized. A minimum of two females per cohort should be randomized in Part 2, with at least one female per cohort receiving active drug.

#### **4.2.1 Recruitment Procedures**

For Part 1, HVs will be identified for potential recruitment using pre-screening enrollment logs, IEC/IRB approved newspaper/radio advertisements and mailing lists prior to consenting to take place on this study.

For Part 2, study sites will search their database of CHB patients for potentially suitable patients. Patients will be identified for potential recruitment using pre-screening enrollment logs. In case the study sites will use newspaper/Social Network Service/poster advertisements, mailing lists or other distributable documents to recruit patients, the Sponsor will ensure that these documents have been reviewed and approved by the IEC/IRB prior to use.

#### **4.2.2 Inclusion Criteria**

##### **4.2.2.1 Part 1: SAD and MAD in Healthy Volunteers**

HVs must meet the following criteria for study entry:

1. Healthy male and female subjects, 18 to 65 years of age, inclusive. Healthy status is defined by absence of evidence of any active or chronic disease following a detailed medical and surgical history, a complete physical examination including vital signs, 12-lead ECG, hematology, blood chemistry, and urinalysis.
2. Informed of, and willing and able to comply with, all of the protocol requirements and the investigational nature of the study, and have signed an informed consent form (ICF) in accordance with institutional and regulatory requirements.

3. For women of childbearing potential: agreement to remain abstinent (refrain from heterosexual intercourse) or use two approved contraceptive methods, of which one must be a barrier method and the other should be an established non-barrier form of contraception with a failure rate of < 1% per year, during the treatment period and for at least one month after the last dose of study drug.
  - a. A woman is considered to be of childbearing potential if she is post menarcheal, has not reached a post menopausal state ( $\geq 12$  continuous months of amenorrhea with no identified cause other than menopause), and has not undergone surgical sterilization (removal of ovaries and/or uterus).
  - b. Examples of contraceptive methods with a failure rate of < 1% per year include bilateral tubal occlusion, male sterilization, established proper use of hormonal contraceptives that inhibit ovulation, hormone-releasing IUDs, and copper IUDs.
  - c. The reliability of sexual abstinence should be evaluated in relation to the duration of the clinical trial and the preferred and usual lifestyle of the patient. Periodic abstinence (e.g., calendar, ovulation, symptothermal, or post ovulation methods) and withdrawal are not acceptable methods of contraception.
4. Male subjects must be willing to use two methods of contraception with their partners, one of which must be a barrier method (i.e. condom), for the duration of the study and for one month after the last dose of study medication. Other acceptable forms of contraception for this study include vasectomy, bilateral tubal occlusion, intrauterine device (IUD) or proper use of hormonal contraceptives. Periodic abstinence is not considered an adequate form of contraception. Men must refrain from donating sperm during this same period.
5. Negative pregnancy test on Day -1 for female subjects.
6. A body mass index (BMI) between 18 to 32 kg/m^2, inclusive.
7. Non-smokers, or use of < 10 cigarettes (or equivalent nicotine-containing product) per day.
8. Negative anti-nuclear antibody (ANA) test; or positive with dilutions not greater than 1:40 and with no associated history or symptoms of potential connective tissue disease or other immune-mediated diseases.

#### **4.2.2.2 Part 2: Chronic Hepatitis B Patients**

Patients must meet the following criteria for study entry:

1. Adult male and female patients, 18 to 65 years of age, inclusive.
2. Informed of, and willing and able to comply with, all of the protocol requirements and the investigational nature of the study, and have signed an informed consent form (ICF) in accordance with institutional and regulatory requirements.
3. A BMI between 21 to 32 kg/m^2, inclusive. Male patients must be above 55 kg and female patients above 45 kg body weight.
4. CHB infection (positive test for HBsAg for more than 6 months prior to randomization).

5. For Cohort 1, 2, 3 and 4: HBsAg detectable at screening.
6. For Cohort 1, 2 and 3: On treatment with tenofovir, entecavir, adefovir, or telbivudine, either as single agents or in combination, for at least 6 months.  
For Cohort 4: HBV treatment naïve or not on any anti-HBV treatment for the past 6 months.
7. For Cohort 1, 2 and 3: HBV DNA < 90 IU/mL for at least 6 months prior to randomization; HBV DNA < 90 IU/mL at screening by Roche Cobas assay.  
For Cohort 4: HBV DNA at screening  $\geq 2 \times 10^4$  IU/mL for HBeAg positive and  $\geq 2 \times 10^3$  IU/mL for HBeAg negative patients.
8. For Cohort 1, 2 and 3: Alanine amino transferase (ALT)  $\leq 1.5 \times$  upper limit of normal (ULN) during the 6 months prior to randomization confirmed by two measurements separated by at least 14 days (one of the ALT measurements can be done at screening); ALT at screening  $\leq 1.5 \times$  ULN.  
For Cohort 4: ALT and aspartate aminotransferase (AST) at screening and Day -1 visit:  $\leq 5 \times$  ULN.
9. Screening laboratory values (including hematology, chemistry, urinalysis) obtained up to 28 days prior to first study treatment within acceptable range or judged to be not clinically significant by the Principal Investigator (PI) and Medical Monitor.
10. Gamma glutamyl transpeptidase (GGT), alkaline phosphatase (ALP), albumin, total and direct bilirubin within normal range or judged to be not clinically significant by the Investigator and Medical Monitor at screening.
11. Negative ANA test, or positive with dilutions not greater than 1:40 and with no associated history or symptoms of potential connective tissue disease or other immune-mediated diseases.
12. Liver biopsy, Fibroscan® or equivalent elastography test obtained within 6 months prior to randomization demonstrating liver disease consistent with chronic HBV infection with absence of cirrhosis and absence of extensive bridging fibrosis (cirrhosis or extensive bridging fibrosis are defined as  $\geq$  Metavir 3, recommended cutoff for fibroscan 8.5 kPa).
13. For women of childbearing potential: agreement to remain abstinent (refrain from heterosexual intercourse) or use two approved contraceptive methods, of which one must be a barrier method and the other should be an established non-barrier form of contraception with a failure rate of < 1% per year, during the treatment period and for at least one month after the last dose of study drug.
  - a. A woman is considered to be of childbearing potential if she is post-menarcheal, has not reached a post-menopausal state ( $\geq 12$  continuous months of amenorrhea with no identified cause other than menopause), and has not undergone surgical sterilization (removal of ovaries and/or uterus).
  - b. Examples of contraceptive methods with a failure rate of < 1% per year include bilateral tubal occlusion, male sterilization, established proper use of hormonal contraceptives that inhibit ovulation, hormone-releasing IUDs, and copper IUDs.

- c. The reliability of sexual abstinence should be evaluated in relation to the duration of the clinical trial and the preferred and usual lifestyle of the patient. Periodic abstinence (e.g., calendar, ovulation, symptothermal, or post-ovulation methods) and withdrawal are not acceptable methods of contraception.
14. For men: agreement to remain abstinent (refrain from heterosexual intercourse) or use contraceptive measures, and agreement to refrain from donating sperm, as defined below:
  - a. With female partners of childbearing potential or pregnant female partners, men must remain abstinent or be willing to use two methods of contraception with their partners, one of which must be a condom and the other should be an established form of contraception, during the treatment period and for at least one month after the last dose of study drug to avoid exposing the embryo. Other acceptable forms of contraception include vasectomy, bilateral tubal occlusion, IUD or proper use of hormonal contraceptives (e.g. contraceptive pills). Men must refrain from donating sperm during this same period.
  - b. The reliability of sexual abstinence should be evaluated in relation to the duration of the clinical trial and the preferred and usual lifestyle of the patient. Periodic abstinence and withdrawal are not acceptable methods of contraception.
15. Negative pregnancy test on Day -1 for female patients.

#### **4.2.3            Exclusion Criteria**

##### **4.2.3.1        Part 1: SAD and MAD in Healthy Volunteers**

HVs who meet any of the following criteria will be excluded from study entry:

1. Pregnant (positive pregnancy test) or lactating women, and male partners of women who are pregnant or lactating.
2. History of immunologically mediated disease (e.g., inflammatory bowel disease, idiopathic thrombocytopenic purpura, lupus erythematosus, autoimmune hemolytic anemia, scleroderma, severe psoriasis, rheumatoid arthritis, multiple sclerosis, or any other autoimmune disease).
3. History or symptoms of any clinically significant disease including (but not limited to), neurological, cardiovascular, endocrine, respiratory, hepatic, ocular, or renal disorder (as per investigator's judgment).
4. Personal or family history of congenital long QT syndrome or sudden cardiac death.
5. Evidence of an active or suspected cancer or a history of malignancy, where in the Investigator's opinion, there is a risk of recurrence.
6. History of having received or currently receiving any systemic anti-neoplastic (including radiation) or immune-modulatory treatment (including systemic oral or inhaled corticosteroids, IFN or PEG-IFN) within the 8 weeks prior to the first dose of study drug or the expectation that such treatment will be needed at any time during the study. Eye drop-containing and infrequent inhaled corticosteroids are permissible up to 4 weeks prior to the first dose of study drug.

7. History of clinically significant thyroid disease; also, subjects with clinically significant elevated thyroid-stimulating hormone (TSH) concentrations at screening.
8. Any confirmed clinically significant allergic reactions (anaphylaxis) against any drug, or multiple drug allergies (non-active hay fever is acceptable).
9. History of clinically significant psychiatric disease, especially major depression (significant psychiatric disease is defined as treatment with an antidepressant medication or a major tranquilizer at therapeutic doses for major depression or psychosis, respectively, or any history of the following: a suicide attempt, hospitalization for psychiatric disease, or a period of disability due to a psychiatric disease).
10. Clinically significant acute infection, e.g., influenza, local infection or any other clinically significant illness within two weeks of randomization.
11. History of clinically significant GI disease including inflammatory bowel disease, peptic ulcer disease, GI hemorrhage.
12. Confirmed systolic blood pressure (BP) greater than 140 or less than 90 mmHg, and diastolic BP greater than 90 or less than 50 mmHg at screening (based on the average of 3 separate resting BP measurements, properly measured with well-maintained equipment, after at least 5 minutes rest).
13. Clinically relevant ECG abnormalities on screening ECG: e.g.,
  - a. QTc interval (QTcF > 450 msec or < 300 msec)
  - b. Notable resting bradycardia (HR < 45 bpm), or HR > 90 bpm
  - c. Difference between highest and lowest of any screening QTc > 30 msec
  - d. ECGs with documented machine errors in the interval duration assessments
  - e. ECG with QRS and / or T-wave judged to be unfavorable for a consistently accurate QT measurement (e.g., neuromuscular artifact that cannot be readily eliminated, arrhythmias, indistinct QRS onset, low amplitude T-wave, merged T- and U-waves, prominent U-waves)
  - f. Evidence of atrial fibrillation, atrial flutter, complete bundle branch block, Wolf-Parkinson-White Syndrome, or cardiac pacemaker.
14. Any of the following laboratory parameters prior to dosing:
  - a. White blood cells (WBC) < 3000 cells/mm^3
  - b. Neutrophil count < 1500 cells/mm^3
  - c. Platelet count < 140,000 cells/mm^3
  - d. Activated partial thromboplastin time (aPTT) > 40 seconds, international normalized ratio (INR) > 1.2
  - e. Hb < 12 g/dL in females or 13 g/dL in males
15. Abnormal renal function including serum creatinine > ULN or calculated CrCl < 70 mL/min (using the Cockcroft Gault formula).

16. ALT or AST values at screening above ULN and judged clinically significant by the Investigator.
17. Positive results for anti-mitochondrial antibody (AMA), anti-smooth muscle antibody (ASMA) or thyroid peroxidase antibody.
18. Positive Hepatitis A virus antibody (HAV Ab IgM), Hepatitis B surface antigen (HBsAg), Hepatitis C antibody (HCV Ab), or positive for human immunodeficiency virus (HIV) at screening.
19. Any other clinically significant abnormalities in laboratory test results at screening. In the case of uncertain or questionable results, tests performed during screening may be repeated before randomization to confirm eligibility or judged to be clinically irrelevant for healthy subjects.
20. History of alcohol abuse (consumption of more than 2 standard drinks per day on average; 1 standard drink = 10 grams of alcohol) and/or drug abuse within one year of randomization. Alcohol consumption will be prohibited at least 48 hours before screening, 48 hours before admission until discharge from the clinic, and 48 hours before each scheduled visit.
21. Positive test for drugs of abuse or positive alcohol test at screening or Day – 1.
22. Any clinically significant concomitant disease or condition that could interfere with, or for which the treatment of might interfere with, the conduct of the study, or that would, in the opinion of the Investigator, pose an unacceptable risk to the subject in this study.
23. Use of any medication (prescription or over-the-counter [OTC], including health supplements, vitamins or herbal remedies) within the 2 weeks prior to the first dosing or within 5 half-lives of the medication prior to first dosing (whichever is longer). Exceptions may be made on a case-by-case basis following discussion and agreement between the Investigator and the Sponsor.
24. Participation in an investigational drug or device study within 90 days prior to randomization.
25. Donation or loss of blood over 500 mL, or administration of any blood product, within 90 days prior to starting study medication.
26. Subjects under judicial supervision, guardianship or curatorship.
27. Any medical or social condition which may interfere with the subject's ability to comply with the study visit schedule or the study assessments.

#### **4.2.3.2 Part 2: Chronic Hepatitis B Patients**

Patients who meet any of the following criteria will be excluded from study entry:

1. Pregnant (positive pregnancy test) or lactating women.
2. History of liver cirrhosis.
3. History or other evidence of bleeding from esophageal varices.

4. Decompensated liver disease (e.g., Child-Pugh Class B or C clinical classification or clinical evidence such as ascites or varices).
5. History or other evidence of a medical condition associated with chronic liver disease other than HBV infection (e.g., hemochromatosis, autoimmune hepatitis, alcoholic liver disease, toxin exposure, thalassemia, nonalcoholic steato-hepatitis, etc.). A clinical diagnosis of fatty liver is allowed provided that non-alcoholic steatohepatitis (NASH) has been excluded by liver biopsy.
6. Documented history or other evidence of metabolic liver disease within one year of randomization.
7. Positive test for Hepatitis A virus (IgM anti-HAV), Hepatitis C virus (HCV), Hepatitis D virus, Hepatitis E virus (HEV), or human immunodeficiency virus (HIV).
8. Expected to need systemic antiviral therapy other than that provided by the study at any time during their participation in the study, with the exception of oral therapy for Herpes simplex virus type I (HSV I) or HSV II.
9. History of or suspicion of hepatocellular carcinoma or alpha fetoprotein  $\geq 13$  ng/mL at screening.
10. History of immunologically mediated disease (e.g., inflammatory bowel disease, idiopathic thrombocytopenic purpura, lupus erythematosus, autoimmune hemolytic anemia, scleroderma, severe psoriasis, rheumatoid arthritis, multiple sclerosis, or any other autoimmune disease).
11. History of clinically significant cardiovascular (including postural hypotension), endocrine, renal, ocular, pulmonary or neurological disease (as per Investigator's judgment).
12. History of clinically significant GI disease including inflammatory bowel disease, peptic ulcer disease, GI hemorrhage, or history of pancreatitis.
13. History of clinically significant psychiatric disease, especially major depression (significant psychiatric disease is defined as treatment with an antidepressant medication or a major tranquilizer at therapeutic doses for major depression or psychosis, respectively, or any history of the following: a suicide attempt, hospitalization for psychiatric disease, or a period of disability due to a psychiatric disease).
14. Active or suspected cancer or a history of malignancy, where in the Investigator's opinion, there is a risk of recurrence.
15. History of having received or currently receiving any systemic anti-neoplastic (including radiation) or immune-modulatory treatment (including systemic oral or inhaled corticosteroids, IFN or PEG-IFN) within the 8 weeks prior to the first dose of study drug or the expectation that such treatment will be needed at any time during the study. Eye drop-containing and infrequent inhaled corticosteroids are permissible up to 4 weeks prior to the first dose of study drug.

Cohort 4: Concurrent HBV treatments.

16. History of organ transplantation.

17. Clinically significant thyroid disease; also, patients with clinically significant elevated TSH concentrations at screening.
18. Any confirmed clinically significant allergic reactions (anaphylaxis) against any drug, or multiple drug allergies (non-active hay fever is acceptable).
19. Clinically significant acute infection (e.g., influenza, local infection) or any other clinically significant illness within 2 weeks of randomization.
20. Clinically relevant ECG abnormalities on screening ECG.
21. Any of the following laboratory parameters at screening:
  - a. WBC < 3,000 cells/mm^3
  - b. Neutrophil count < 1500 cells/mm^3
  - c. Platelet count < 140,000 cells/mm^3
  - d. aPTT > 40 seconds, INR > 1.2
  - e. Hb < 12 g/dL in females or 13 g/dL in males
22. Abnormal renal function including serum creatinine > ULN or calculated CrCl < 60 mL/min (using the Cockcroft Gault formula).
23. Positive results for AMA, ASMA or thyroid peroxidase antibody.
24. Participation in an investigational drug or device study within 30 days prior to randomization.
25. Donation or loss of blood over 500 mL, or administration of any blood product, within 90 days prior to starting study medication.
26. History of alcohol abuse (consumption of more than 2 standard drinks per day on average; 1 standard drink = 10 grams of alcohol) and/or drug abuse within one year of randomization.
27. Positive test for drugs of abuse or positive alcohol test at screening or Day -1. For positive cannabinoids test, the eligibility is at the Investigator's discretion.
28. Patients under judicial supervision, guardianship or curatorship.
29. Any medical or social condition which may interfere with the patient's ability to comply with the study visit schedule or the study assessments.

#### **4.3 METHOD OF TREATMENT ASSIGNMENT AND BLINDING**

This study is observer-blinded. This means that the subjects (HV and patients), the Investigator(s), and all individuals in direct contact with the HVs/patients at the investigative sites will be blinded. For Part 1 only, the pharmacy staff handling the study drug distribution will be unblinded.

This study is Sponsor open; members of the Sponsor's study team will be unblinded. This may exclude CRO staff in direct contact with the study sites.

#### **4.3.1 Part 1: SAD and MAD in Healthy Volunteers**

In each Cohort of Part 1, 10 study subjects will be randomized 4:1 to RO7020531 or to placebo. Each cohort of HVs in Part 1 will randomize a minimum of two females, with at least one female receiving active drug.

The list of randomized treatment assignments will be generated by Roche or its designee. The randomized treatment assignment will be allocated from the list sequentially to subjects in the order in which they are randomized. For each dose cohort (in SAD only), the randomization will be designed such that of the first 2 subjects, 1 will receive active drug, and the other will receive placebo. The remaining 8 subjects in the cohort will be randomized such that 7 receive active drug and 1 receives placebo. The treatment allocation will be managed by the unblinded pharmacist and will be based on the randomization code list.

To allow informed recommendations or decisions regarding the dose decisions in this study, an integrated assessment of the available data on PK, select PD, safety and tolerability will be made prior to each dose decision.

In exceptional cases, (e.g. if deemed important for dose decisions or for the more thorough evaluation of safety-related concerns that may impact dosing of future subjects on this or other currently conducted or shortly to start studies involving administration of RO7020531) and in the interest of the subjects' safety, the investigator may be unblinded after approval by the Clinical Pharmacologist.

The investigator will receive a set of sealed treatment codes. These may have the form of sealed envelopes or scratch codes. If the identity of the test medication needs to be known in order to manage the subject's condition, the treatment code for that subject may be broken.

As per health authority reporting requirements, the sponsor will break the treatment code for all unexpected SAEs (see Section 5.1) that are considered by the investigator to be related to study drug. All treatment code breakages should be documented in the study file. Treatment codes should not be broken except in emergency situations and, if possible, the responsible clinical pharmacologist should be contacted before the code is opened. At the final monitoring visit, the unused code labels will be counted and checked and a statement to the effect that all are intact (or not as the case may be) will be made by the monitor; this statement will be included or referred to in the final study report. All code labels will be destroyed by the investigator site after verification by the study monitor, and once permission is granted by Roche.

Whenever disclosure of the identity of the test medication is necessary, adequate procedures will be in place to ensure integrity of the data. Any unblinding at the investigating site, will be documented in the study report with date, reason for identifying the drug and the name of all the person(s) who had to be unblinded.

### **4.3.2            Part 2: Chronic Hepatitis B Patients**

In each Cohort of Part 2, patients will be randomized 4:1 to RO7020531 or to placebo. Each cohort of patients in Part 2 will randomize a minimum of two females, with at least one female receiving active drug. The patient randomization numbers will be generated by the interactive voice/web response system (IxRS) according to specifications provided by the Sponsor to the external randomization vendor. Patients and all study site personnel will be blinded to treatment assignment throughout the Part 2 of the study until all patients have completed their treatment period or discontinued prematurely. Members of the Sponsor's study team will be unblinded. This may exclude CRO staff in direct contact with the study sites.

If unblinding at the site is necessary for patient management (in the case of an SAE), the Investigator will be able to break the treatment code by contacting the IxRS. Treatment codes should not be broken except in emergency situations. If the Investigator wishes to know the identity of the study drug for any other reason, he or she should contact the Medical Monitor directly before the code is broken, if possible. The Investigator should document and provide an explanation for any premature unblinding (e.g., accidental unblinding, unblinding due to a SAE).

As per Health Authority reporting requirements, the Sponsor will break the treatment code for all unexpected SAEs (see Section 5.1) that are considered by the Investigator to be related to study drug.

Whenever disclosure of the identity of the test medication is necessary, adequate procedures will be in place to ensure integrity of the data. Any unblinding at the investigating site end, will be documented in the study report with date, reason for identifying the drug and the name of all the person(s) who had to be unblinded.

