#### **Part 2: Chronic Hepatitis B Patients**

The total duration of the study will be up to 16 weeks (from screening through study completion) for each randomized patient as follows:

- Screening: Up to 28 days;
- Dosing period: 6 weeks;
- Follow up: 6 weeks after last dosing.

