## **Part 2: Chronic Hepatitis B Patients**

A follow-up period of 6 weeks will occur for all treatment arms. All patients who complete the 6-week treatment period or discontinue from the study treatment early will be asked to return for follow-up visits at Week 9 and Week 12 and complete assessments as specified in the SoA ([Appendix 1](#)). The visit window for follow-up visits is  $\pm 5$  days.

After the last follow-up visit (Week 12), AEs should be followed as outlined in Section [5.1](#) and [5.5](#).

The last follow-up visit (Week 12) will be reported in eCRF as patient's study completion.

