All patients who discontinue the study treatment prematurely should complete the 6-week follow-up period (starting from the date of the last dose taken) as per SoA (Appendix 1). The primary reason for premature study drug discontinuation should be documented on the appropriate eCRF.

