### **5.3 METHODS AND TIMING FOR CAPTURING AND ASSESSING SAFETY PARAMETERS**

The Investigator is responsible for ensuring that all AEs (see Section [5.1.1](#) for definition) are recorded on the AE eCRF and reported to the Sponsor in accordance with instructions provided in this section and in Section [5.1](#) and [5.5](#).

For each AE recorded on the AE eCRF, the Investigator will make an assessment of seriousness (Section [5.1.2](#) for seriousness criteria), severity (Section [5.3.3](#)), and causality (Section [5.3.4](#)).

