#### **5.3.1 Adverse Event Reporting Period**

Investigators will seek information on AEs at each HV/patient contact. All AE, whether reported by the HV/patient or noted by study personnel, will be recorded in the HV's/patient's medical record. AEs will then be reported on the AE eCRF as follows:

**After informed consent** has been obtained **but prior to initiation of study drug**, only SAEs caused by a protocol-mandated intervention should be reported (e.g., SAE related to invasive procedures such as biopsies). Any other AE should not be reported.

**After initiation of study drug**, all AE, regardless of relationship to study drug, will be reported until the end of follow-up, which is 28 days after the last dose for HVs and 6 weeks after the last dose for patients.

**After the end of follow-up period** (28 days after last dose for HVs and 6 weeks after last dose for patients), investigators should report any deaths, SAE, or other AE of concern that are believed to be related to prior treatment with study drug (see Section 5.5).

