### **5.3.4 Assessment of Causality of Adverse Events**

Investigators should use their knowledge of the HV/patient, the circumstances surrounding the event, and an evaluation of any potential alternative causes to determine whether or not an AE is considered to be related to the study drug, indicating "yes" or "no" accordingly. The following guidance should be taken into consideration:

- Temporal relationship of event onset to the initiation of study drug
- Course of the event, considering especially the effects of dose reduction or discontinuation of study drug
- Known association of the event with the study drug or with similar treatments
- Known association of the event with the disease under study
- Presence of risk factors in the HV/patient or use of concomitant medications known to increase the occurrence of the event
- Presence of non-treatment-related factors that are known to be associated with the occurrence of the event

For patients, causality will be assessed individually for RO7020531 and for NUC analogue(s), if applicable.

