## **6.5 SUMMARIES OF TREATMENT GROUP COMPARABILITY**

Descriptive statistics will be generated for demographic and baseline disease characteristics including sex, race, ethnicity, origin (for Asian HVs/patients only), age, weight, height, body mass index, HBV DNA and HBsAg levels, and HBV history including but not limited to duration of HBV disease, previous HBV treatments, length of time on NUCs. Data for study drug administration and concomitant medication will be listed. The number of HVs/patients who were randomized, discontinued treatment period, completed treatment period, discontinued study and completed the study (including follow-up period) will be summarized.

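### Section 4.3.2 lets the Part 2 patient and site blind lapse when the last patient stops treatment, about 6 weeks before adverse event collection ends; extend it to the last Week 12 visit

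*Combined protocol and SAP*

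**What the plan says.** Section 4.3.2 states that Part 2 patients and site personnel are blinded "throughout the Part 2 of the study until all patients have completed their treatment period or discontinued prematurely". Section 4.3 says that subjects, investigators and site staff are blinded but gives no end date. No other section extends or dates the blind.

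Treatment and follow-up are separate periods:

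- Section 3.1.4 lists, after 6 weeks of dosing, "Follow up: 6 weeks after last dosing".
- Section 6.5 tabulates them as distinct states: "discontinued treatment period, completed treatment period, discontinued study and completed the study (including follow-up period".
- Section 4.6.2.3 says that patients who complete treatment or stop it early "will be asked to return for follow-up visits at Week 9 and Week 12", and it makes Week 12 the patient's study completion.
- Section 4.7.1.1 says that early discontinuers "should complete the 6-week follow-up period (starting from the date of the last dose taken".

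Safety assessment continues through follow-up. Section 5.3.1 collects adverse events until "6 weeks after the last dose for patients". Section 5.3 says "For each AE recorded on the AE eCRF, the Investigator will make an assessment of seriousness", and adds severity and causality. Section 5.3.4 has the investigator "determine whether or not an AE is considered to be related to the study drug", answered yes or no.

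Section 4.3.2 also limits the scope for unblinding. Codes are to be broken only in emergencies. An investigator who wants the code for another reason should, if possible, first contact the Medical Monitor. The Sponsor breaks the code for unexpected related serious events, and every site unblinding is recorded in the study report.

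**The concern.** Safety and tolerability are the primary variables (Section 6.6). Whether an event is elicited, how severe it is rated and whether it is called drug-related are human judgements, and knowing the arm can shift them. The written commitment to blind the people making those judgements ends before the judgements do.

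The most exposed judgement is the reading of modest ALT rises. Section 5.2.1 says that self-limited rises of 2 to 3 times baseline probably reflect treatment response rather than toxicity, a reading that knowledge of the arm feeds directly. Cohort 4 patients are viraemic and may enter with ALT up to 5 times the upper limit of normal (Section 4.2.2.2). Blood chemistry is scheduled for them at Weeks 9 and 12 (Appendix 1).

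There is a practical side too. Section 4.3.2 asks investigators to document and explain premature unblinding. With the blind ending at the last end of treatment, a code opened during late follow-up would not clearly count as premature.

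**Working it through.** **1. The protocol's own timeline.** Screening 4 weeks + dosing 6 + follow-up 6 = 16 weeks, as Section 3.1.4 states. From randomization, 6 + 6 = 12 weeks, which matches the expected last observation 12 weeks after the last Part 2 randomization.

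**2. The gap for the last patient.** End of treatment is Day 42 and Week 12 is Day 84, so the gap is 84 − 42 = 42 days, half of the 84 days after randomization. The end-of-treatment visit may fall on Day 39/40 and Week 12 has a ±5-day window. The gap therefore runs from 84 − 5 − 42 = 37 days to 84 + 5 − 40 = 49 days.

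**3. Who could be exposed.** Take the clause to mean all Part 2 patients. By 1 May 2020, 30 patients in Cohorts 1–3 and 9 in Cohort 4 had been dosed (Section 1.2.2). Cohort 4 has 8–12 active plus 2–3 placebo (Section 4.4.2.1), that is 10 to 15 patients, so 1 to 6 remained to be dosed.

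Assumptions not in the documents:

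- the n remaining patients enrol evenly over T weeks, with T from 6 to 30;
- the 9 already dosed have finished follow-up when the last patient stops treatment;
- for the upper bound, every code opens on that day.

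With spacing g = T/(n − 1), the patient k places before the last has max(0, 6 − k·g) weeks of follow-up left. The last patient (k = 0) always has 6.

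| Cohort 4 size | n | T (weeks) | g | Patient-weeks after the stated end of blind | Patients | Share of Cohort 4 follow-up |
|---|---|---|---|---|---|---|
| 15 | 6 | 6 | 1.2 | 6 + 4.8 + 3.6 + 2.4 + 1.2 = 18.0 | 5 | 18.0/90 = 20% |
| 15 | 6 | 12 | 2.4 | 6 + 3.6 + 1.2 = 10.8 | 3 | 10.8/90 = 12% |
| 15 | 6 | 26 | 5.2 | 6 + 0.8 = 6.8 | 2 | 6.8/90 = 7.6% |
| 15 | 6 | 30 | 6 | 6.0 | 1 | 6.0/90 = 6.7% |
| 12 | 3 | 6 | 3 | 6 + 3 = 9.0 | 2 | 9.0/72 = 12.5% |
| 12 | 3 | 12 or more | 6 or more | 6.0 | 1 | 6.0/72 = 8.3% |
| 10 | 1 | – | – | 6.0 | 1 | 6.0/60 = 10% |

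The denominators are cohort size × 6 weeks. Against all Part 2 adverse event time, (30 + 15) × 12 = 540 patient-weeks, the 15-patient rows give 18.0/540 = 3.3% down to 6.0/540 = 1.1%.

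**4. Placebo patients among them.** At 4:1 allocation, 0.2 × (1 to 5) = 0.2 to 1.0 expected.

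**5. The lower bound.** No section schedules code release. If no code is opened before follow-up ends, the number exposed is 0.

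**The case against.** Two stronger readings are tempting, and the documents support neither.

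- A reader might infer that the sentence contradicts itself by naming both the whole of Part 2 and the end of treatment. In ordinary English the second clause limits the first, leaving one end-point. The opening words suggest a longer blind but do not establish one. The difficulty is that the single end-point comes too early.
- A reader might infer that sites will be unblinded at the end of treatment. Nothing instructs this. The text stops promising the blind; it does not release codes. The emergency-only restriction carries no time limit, and every site unblinding must be documented. The counts above are therefore upper bounds.

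The case that little turns on this is also strong:

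- No hypothesis is tested (Section 6), and the Sponsor's team is open by design and may upgrade causality and seriousness (Section 5.6).
- Flu-like symptoms usually start after the first to third dose (Section 1.3.2), and the active metabolite has a half-life of about 4 hours (Section 1.2.2). The main known drug effects thus fall within blinded treatment.
- Viral outcomes are laboratory assays. Liver events have numeric reporting thresholds (Section 5.3.5.6), and flares and virological breakthrough are to be reported as adverse events (Section 5.3.5.9).

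All of this stands, and it limits the size of the point. It leaves elicitation, severity, relatedness and ALT rises below the flare threshold open to influence. It does not bring the end of the blind into line with the end of safety assessment.

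The accrual figures can also be challenged. Section 1.2.2 says only that 9 patients had been dosed. If the tenth started soon after the ninth, the ninth would still be in follow-up and the 10-patient row would be too low. Finally, the clause does not say whether it covers all of Part 2 or each cohort. A by-cohort reading would affect more patients, but the documents give no dates from which to count them.

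**Conclusion.** The point holds as a cheap improvement to one sentence. As written, the patient and site blind is promised only to the last patient's end of treatment, about 42 days (37 to 49 with visit windows) before that patient's safety follow-up ends. Between 0 and about 5 Cohort 4 patients could be followed unblinded, at most 18 patient-weeks, with 1.0 or fewer expected on placebo. The range rests on reading the clause as covering all of Part 2, on even accrual over 6 to 30 weeks, and on the first 9 Cohort 4 patients having completed follow-up. No error rate, sample size or dose decision is affected. The risk is some bias in investigator judgements of late adverse events in a descriptive safety comparison.

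**What to change.** Replace the end-point in Section 4.3.2 with wording such as:

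*Patients and site staff stay blinded to allocation until the last Part 2 patient, counting all cohorts, has had the Week 12 follow-up visit or has withdrawn from the study.*

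Preferably continue the blind to database lock, so that adverse event queries are also resolved blind. Section 6 already makes lock a condition for the complete analysis, but it does not name it as an unblinding point; that part is a recommendation. The Week 12 visit alone would cover adverse event collection. Leave the emergency IxRS route, the Medical Monitor route and the Sponsor's code break for unexpected related serious events unchanged.

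The cost is later disclosure: about 6 weeks beyond what the present text permits, plus the time to lock (not given) if lock is used. Patients in earlier cohorts would wait longer still if the Sponsor had intended release by cohort. The complete analysis is not delayed, because it already waits for follow-up and lock. Dose decisions are unaffected, because the Sponsor's team is unblinded. The change protects site and patient assessment only.
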